5.13.2 Stakeholder Questionnaire

Key stakeholders (healthcare workers including nurses, primary care providers and other relevant personnel) will be contacted via email with a questionnaire to explore attitudes to tampons as a means of sample collection for microbial testing. Individuals involved with the trial with experience working with the DDT will be contacted, as well as independent individuals who have signed up to existing mailing lists held at Lindus Health. The stakeholder questionnaire will collect an individual's job title and organisation only, and no further personal data will be collected. Completion of the questionnaire will be voluntary.

5.14. Sample Handling

Samples taken as part of the trial are research samples for analysis under this protocol and will be destroyed once analysis is completed. If explicit consent for use for future research is given, anonymised DNA and/or RNA will be kept for future ethically approved research projects.

5.14.1. Sample processing in the UK

All samples from participants in the UK will be sent to an accredited laboratory in the UK for analysis.

5.14.2. Sample processing in Italy

All samples from participants in Italy will be sent to an accredited laboratory in Italy for analysis.

5.14.3. Sample Analysis and storage

The accuracy of HPV and STI testing using menstrual tampons will be evaluated by comparing the results of the tampon self-sampling and self-swab sampling to the results of the clinician swab sampling. Sensitivity, specificity, positive predictive value (PPV), and negative predictive value (NPV) will be calculated to assess the performance of the tampon and swab sampling methods compared to the clinician swab as the gold standard.

There is no single assay test kit that is able to reliably test for all the organisms of interest in this trial, we have therefore chosen assays that have been proven to reliably detect the organisms of interest. All of the samples collected will be analysed using the following assays::

Infection	HPV	Chlamydia/Gonorrhoea	Bacterial Vaginosis
Assay	Hologic's APTIMA HPV	Hologic's APTIMA AC2	Cepheid MPV assay
Description and justification for use	
Hologic APTIMA HPV assay is a well-established sensitive assay utilised by multiple centres involved in public healthcare and is included in the 2020 list of HPV assays suitable for primary cervical cancer screening¹². This is a nucleic acid amplification test for qualitative detection of viral mRNA E6 and E7 genes of high-risk HPV genotypes are known oncogenes. This assay utilises transcription-mediated amplification (TMA) based (Aptima) amplification.
	
The APTIMA AC2 assay, is a nucleic acid amplification test utilised in various public healthcare settings. This assay is specifically designed for the qualitative detection of sexually transmitted infections (STIs), specifically Chlamydia and Gonorrhoea. It employs transcription-mediated amplification (TMA), a technology associated with the Aptima system. The test targets specific nucleic acid sequences related to STIs, providing sensitive and accurate results.¹³ The APTIMA AC2 assay is recognized for its reliability and is widely used for STI screening and diagnosis in clinical settings.
	
The Cepheid MPV assay has been chosen as it has proven effectiveness for detecting organisms associated with bacterial vaginosis (Atopobium spp, BVAB2, Megaspheera) with high sensitivity and specificity¹⁴. It is a widely used test because of the short turnaround time of this assay (result within 60 minutes), In addition, because of this speed of turnaround it is appropriate for point of care testing (POCT) use.

Samples obtained from participants will be utilised solely for the explicit purpose of this project. In the event that a participant grants explicit consent, prior to destruction these samples will be processed and DNA or RNA extracted, undergo a de-identification process and the extracted DNA or RNA only will be securely stored for potential application in future ethically approved research endeavours. The remaining sample will be systematically and irreversibly destroyed to ensure confidentiality and compliance with ethical standards.

5.15. Early Discontinuation/Withdrawal of Participants

Each participant has the right to withdraw from the trial at any time. Participants leaving the trial before randomisation will be considered screen failures; participants leaving the trial after randomisation will be considered withdrawals.

Following participant withdrawal, no further trial assessments will be performed. The participant will be contacted by a member of the central team and a reason for withdrawal will be requested and documented.

5.16. Definition of End of Trial

End of trial is defined as the last data capture of the last participant.

6 TRIAL PROCEDURES

All participants will receive all three of the trial procedures during their participation in the trial. Participants will be randomised according to sample order for the DDT and self-swab. A gap of at least 1 hour should be left between the at home samples. All materials and instructions for the trial procedures will be provided by the sponsor either directly to the participants or to the trial sites.

6.1. DAYE Diagnostic Tampon (DDT)

The DDT is constructed entirely from woven cotton and consists of an absorbent core wrapped in a protective sleeve. The DDT is loaded in an applicator to aid with insertion. The DDT needs to be worn for a minimum of 20 minutes (and no longer than 4 hours) for collection of the sample, and then once withdrawn should be placed immediately in the provided sterile container with a transport medium and then brought to the clinic visit. Participants should perform the sampling the day before their trial clinic appointment. Participants will receive detailed written and/or verbal instructions on the timing of their samples, the order to perform their samples in, and how to use the tampon. Clear instructions for packaging and sample handling will be provided to the participant.

6.2. Self Swab

Participants will be instructed to insert a swab into their vagina and rotate it three times to collect a sample. After removal, the swab will be placed in a sterile container with a transport medium and returned to the trial team. Participants should perform the self-swab the day before their trial clinic appointment. Participants will receive detailed written and/or verbal instructions on the timing of the samples, the order to perform their samples in and how to use the self-swab. Clear instructions for packaging and sample handling will be provided to the participant.

6.3. Clinician Swab

A clinician will perform a high vaginal swab for HPV and STI testing using a standard protocol that is validated for use for the downstream microbial test, as per local guidelines in each country. The swab will be collected by rotating the swab in the vaginal canal three times and then placing it in a sterile container.

7 SAFETY REPORTING

7.1. Adverse Event Definitions

Adverse Event (AE)	Any untoward medical occurrence in a participant to whom a medicinal product has been administered, including occurrences which are not necessarily caused by or related to that product.
Adverse Reaction (AR)	
An untoward and unintended response in a participant to an investigational medicinal product which is related to any dose administered to that participant.
 
The phrase "response to an investigational medicinal product" means that a causal relationship between a trial medication and an AE is at least a reasonable possibility, i.e. the relationship cannot be ruled out.
 
All cases judged by either the reporting medically qualified professional or the Sponsor as having a reasonable suspected causal relationship to the trial medication qualify as adverse reactions.

Serious Adverse Event (SAE)	
A serious adverse event is any untoward medical occurrence that:
 
· results in death· is life-threatening· requires inpatient hospitalisation or prolongation of existing hospitalisation· results in persistent or significant disability/incapacity· consists of a congenital anomaly or birth defect*. 
Other 'important medical events' may also be considered a serious adverse event when, based upon appropriate medical judgement, the event may jeopardise the participant and may require medical or surgical intervention to prevent one of the outcomes listed above.
 
NOTE: The term "life-threatening" in the definition of "serious" refers to an event in which the participant was at risk of death at the time of the event; it does not refer to an event which hypothetically might have caused death if it were more severe.

	*NOTE: Pregnancy is not, in itself an SAE. In the event that a participant or his/her partner becomes pregnant whilst taking part in a clinical trial or during a stage where the foetus could have been exposed to the medicinal product (in the case of the active substance or one of its metabolites having a long half-life) the pregnancy should be followed up by the investigator until delivery for congenital abnormality or birth defect, at which point it would fall within the definition of “serious”.
Serious Adverse Reaction (SAR)	An adverse event that is both serious and, in the opinion of the reporting Investigator, believed with reasonable probability to be due to one of the trial treatments, based on the information provided.
Suspected Unexpected Serious Adverse Reaction (SUSAR)	A serious adverse reaction, the nature and severity of which is not consistent with the Reference Safety Information for the medicinal product in question set out: 
 · in the case of a product with a marketing authorisation, in the approved summary of product characteristics (SmPC) for that product · in the case of any other investigational medicinal product, in the approved investigator’s brochure (IB) relating to the trial in question.

NB: to avoid confusion or misunderstanding of the difference between the terms “serious” and “severe”, the following note of clarification is provided: “Severe” is often used to describe intensity of a specific event, which may be of relatively minor medical significance. “Seriousness” is the regulatory definition supplied above.

7.2. Assessment of Causality

The relationship of each adverse event to the intervention must be determined by a medically qualified individual according to the following definitions:

- Not Related – where an event is not considered to be related to the intervention
- Possibly – although a relationship to the intervention cannot be completely ruled but the nature of the event, the underlying disease, concomitant medication or temporal relationship make other explanations possible

- Probably – There is evidence to suggest a causal relationship, and the influence of other factors is unlikely.
- Definitely – There is clear evidence to suggest a causal relationship, and other possible contributing factors can be ruled out.

All AEs (SAEs) labelled possibly, probably or definitely will be considered as related to the intervention.

7.3. Procedures for Reporting Adverse Events

We do not anticipate that the trial procedures (DDT or swabs) should result in any adverse events (AEs) but include this section in case such events are reported so that they can be considered for causal links to the trial procedures. Only AEs that are clinically judged by the research site PI as being caused by the trial procedures (related and unexpected) will be reported to the REC that gave favourable opinion.

Participants will be provided with contact information for the trial team and the clinic nurse in the event that they need to report a side effect or medical event from the DDT, self-swab or clinician swab.

Events related to the trial procedures will be collected from the collection of the first trial sample until the final questionnaire is submitted.

7.4. Reporting Procedures for Serious Adverse Events

Any AEs which fall under the definition of a SAE will be reported to the Chief Investigator or designated person within 24 hours, to be reviewed for relatedness and expectedness.

Reports of related and unexpected SAEs (in the opinion of the Chief Investigator or designated person) will be reported to the REC within 15 days of the CI and/or central trial team becoming aware of the event. The Chief Investigator will also notify the Sponsor of all trial SAEs.

Any pregnancy occurring during the trial will result in the immediate discontinuation of the participant if all samples have not yet been taken. Pregnancy in itself is not considered an SAE.

All SAEs will be recorded in the trial EDC platform and any concerns raised immediately with the CI.

There is no requirement for annual safety reports in addition to the information provided through the annual progress report.

Hospitalisations for elective treatment of a pre-existing condition do not need reporting as SAEs.

7.5. Expectedness

There are not anticipated to be any serious adverse events as a result of the DDT.

7.6. Measures to minimise the occurrence of AEs

Participants are advised not to wear the DDT for prolonged periods e.g. no longer than 4 hours, to minimise the risk of Toxic Shock Syndrome.

8 STATISTICS

8.1. Statistical Analysis Plan (SAP)

The plan for the statistical analyses of the trial are outlined below. There is not a separate SAP document in use for the trial.

8.2. Description of Statistical Methods

Descriptive statistics are used to describe the participants in each group. Continuous demographic variables collected at screening will be summarised using arithmetic mean, standard deviation, minimum and maximum values, 25% and 75% quartiles and median. For categorical variables, absolute and relative frequencies are reported.

8.2.1 Primary Endpoints

For the primary endpoints, assessing the diagnostic accuracy of Daye diagnostic tampons for detecting Chlamydia, Gonorrhoea, and BV, and HPV, respectively, the outcome of the tampon sample and the clinician collected sample are compared, with the clinician collected sample serving as the reference. This yields the following contingency table with A, B, C and D referring to the number of participants with the respective outcome on the tampon an clinician collected swabs:

		Daye diagnostic tampon	
		+	-
Clinician collected sample	+	A	B
	-	C	D

The following parameters are calculated:

$$\text{Sensitivity} = \frac{A}{A+B}$$

$$\text{Specificity} = \frac{D}{C+D}$$

$$\text{Positive Predictive Value (PPV)} = \frac{A}{A+C}$$

$$\text{Negative Predictive Value (NPV)} = \frac{D}{B + D}$$

$$\text{Accuracy} = \frac{A + D}{A + B + C + D}$$

The accuracy parameters are indicated per condition, including the number of participants used to calculate the parameter and the corresponding 95% confidence intervals using the Wilson score method. As samples are analysed for RNA/DNA using PCR, a positive result in either collection method very likely indicates the presence of the condition. Samples tested positive from DDT but negative from clinician-collected swabs would be classified as false-positive (C) in this assessment, although they actually are true-positive. This results in an underestimation of PPV, specificity, and accuracy.

Additionally, one-proportion z-tests are conducted to test if the sensitivity for Daye diagnostic tampons is higher than 70% for each condition.

Data from both groups will be pooled for analysis of the primary and secondary endpoints. Additionally, all analyses will be carried out for each subgroup separately.

8.2.2 Secondary Endpoints

The secondary endpoints will be assessed by analysing the items of the questionnaires descriptively at each assessment point in time (pre-sampling and post-sampling). A change score will be calculated for continuous items assessed both pre-sampling and post-sampling, and appropriate statistical methods are used to compare pre- to post-sampling values (e.g., t-test for repeated measurements, Wilcoxon signed-rank test). For categorical items, the absolute and relative frequency of each answer option will be reported, as well as the change between categories pre- and post-sampling where feasible.

The *Occurrence of AEs/SAEs* will be analysed descriptively by indicating the absolute and relative frequency of each AE/SAE over the course of the trial duration.

To assess whether the order of sampling influences the diagnostic accuracy, sensitivity and specificity of self-swabs and DDT are compared using McNemar tests for clinician-swab-positive and -negative samples, respectively. Additionally, Cohen's kappa will be calculated to assess the concordance of results from self-swabs and DDT.

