Trial Aims	
 ● To measure the diagnostic accuracy of the diagnostic tampon in a diverse population of people assigned female at birth. ● To compare the performance of the diagnostic tampon with traditional diagnostic methods to identify potential advantages and challenges. ● To assess the acceptability and usability of the diagnostic tampon among the target population and explore feasibility and clinician acceptability of the diagnostic tampon in clinical practice among key stakeholders. ● To provide evidence-based recommendations for the integration and sustainability of the diagnostic tampon into current health practices.
Trial Objectives	
Primary Objective:
 
 ● Evaluate the diagnostic accuracy of the Daye

	
diagnostic tampon for detecting Chlamydia, Gonorrhoea, BV and HPV, specifically demonstrating a sensitivity of more than 70% for DDT.
 
Secondary objectives:
 
 ● Assess the usability of the DDT (via ASQ). ● Explore participants' views of the usability and acceptability of the DDT. ● Assess whether the DDT is a preferred sampling method for participants. ● Assess if the order of sample collection (self-swab vs DDT) impacts diagnostic accuracy. ● Understand the health economic consequences of using the DDT for STI, BV and HPV testing. ● Explore stakeholder attitudes to tampons as a means of sample collection for microbial testing. ● Assess the occurrence of AEs/SAEs as a result of tampon sampling. 
Exploratory objective:
 
 ● Explore the relationship between duration of wear and diagnostic accuracy.
Sample Size	
350 participants
 
Group 1: 50 participants with a recent confirmed HPV+ diagnosis (UK and Italy)
 
Group 2: 300 participants from the general population (UK only)

Procedures	
All participants will have 3 samples taken: the DAYE Diagnostic Tampon (DDT), a vaginal self-swab and a clinician taken vaginal swab that is validated for use for the downstream microbial test.

Randomisation	
All participants will be randomised using block randomisation according to sample order for the DDT and self-swab:
 
 ● Group A: Approximately half the participants will perform the self-swab followed by the DDT. ● Group B: Approximately half the participants will perform the DDT followed by the self-swab

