3. TRIAL DESIGN

A diagnostic trial comparing the diagnostic accuracy, usability and acceptability of the DAYE Diagnostic Tampon (DDT) compared to standard vaginal self-swabs and clinician administration of a vaginal swabs. Diagnostic accuracy will be compared for detection of Chlamydia, Gonorrhoea, BV & HPV.

A total of 350 eligible participants will be enrolled into the trial in the UK and Italy. To adequately assess DDT performance on specificity and sensitivity, participants will be recruited from one of two groups:

- Group 1: 50 participants with a recent confirmed HPV diagnosis (UK and Italy)
- Group 2: 300 participants from the general population (UK only)

All participants will be randomised according to sample order for the DDT and self-swab using block randomisation:

[figure not shown]
- Group A: Approximately half the participants will perform the self-swab followed by the DDT.
- Group B: Approximately half the participants will perform the DDT followed by the self-swab

Pre-screening, informed consent, screening and eligibility assessments may occur online or in person. Randomisation will be performed at the point of enrolment by a member of the trial team using a pre-generated list of treatment allocation blocks. Some demographic information and medical history will be collected at baseline. All eligible participants will be provided with a trial kit containing the DDT and self-swab and attend at least 1 clinic visit where they will have a clinician taken vaginal swab as part of their participation in the trial. Participants will also provide answers to questionnaires at baseline and after all sampling is complete. Participants will enter data directly into the EDC platform or via paper questionnaires completed in-person at the clinic visit and entered into the EDC platform by trained staff. Participation in the trial is expected to last approximately 2-4 weeks (dependent on timing of clinic appointment(s)). All samples collected during the trial will be sent to a central accredited laboratory for analysis, either in the UK or Italy i.e., samples will be analysed in the country they were collected.

[figure not shown]

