5.6. Registration / Enrolment & Randomisation

Once eligibility has been confirmed by the site team participants will be enrolled and randomised to a sampling order using a block randomisation method. Participants in group 1 will be stratified by country. Randomisation will be performed at the point of enrolment by a member of the trial team using a pre-generated list of treatment allocation blocks.

Participants will be assigned a trial number in the format STP-[UK/IT]-NUMBER.

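### The order-of-sampling objective is given McNemar tests and kappa of self-swab against DDT, which compare devices; the randomised sequence (Group A v Group B) does not enter the order analysis

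*Protocol*

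**What the plan says.** The objective in section 2 is: "Assess if the order of sample collection (self-swab vs DDT) impacts diagnostic accuracy". Section 3 provides the design for it: "All participants will be randomised according to sample order for the DDT and self-swab using block randomisation". Allocation is about 1:1, with Group A taking the self-swab before the DDT and Group B the reverse. Section 5.6 repeats that randomisation is to a sampling order.

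The analysis is in section 8.2.2: "To assess whether the order of sampling influences the diagnostic accuracy, sensitivity and specificity of self-swabs and DDT are compared using McNemar tests". The tests are run among clinician-positives for sensitivity and among clinician-negatives for specificity. The next sentence adds that "Cohen's kappa will be calculated to assess the concordance of results from self-swabs and DDT".

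Nothing else in section 8 compares A with B. The pooling rule in section 8.2.1 ("Data from both groups will be pooled for analysis of the primary and secondary endpoints") and the separate-group analyses in sections 8.2.1 and 8.5 follow the division into Group 1 (recent HPV diagnosis) and Group 2 (general population). Section 8.2.4 does plan an unpaired Fisher's exact test on sensitivity and specificity, but between countries. Section 8.1 says that no separate SAP is in use.

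**The concern.** Each participant has one sequence only, so order is a between-participant factor. A McNemar table of self-swab against DDT is a within-participant contrast of devices. Its null hypothesis is that the two devices have equal sensitivity (or specificity), averaged over whatever sequences occurred. Kappa likewise measures agreement between devices. Neither changes if the A/B labels are shuffled, so neither can estimate what sequence does.

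Two wrong conclusions are possible. A real order effect could be reported as absent, and a difference between the devices could be reported as an effect of order.

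**Working it through.** **Inputs.** Section 8.3 gives prevalences of 70% (HPV, Group 1), 10% (STI, Group 2) and 30% (BV, Group 2), with final sizes of 50 and 300. Expected clinician-positives, with no losses and about half in each sequence:
- STI: 0.10 × 300 = 30, so 15 per sequence
- HPV, Group 1: 0.70 × 50 = 35, so 17 or 18 per sequence
- BV: 0.30 × 300 = 90, so 45 per sequence

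No HPV prevalence is given for Group 2, so none is added. Section 8.7 sets a two-sided 5% level. The effect sizes below are assumptions; the protocol gives none for order.

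**The plan's own figure.** There is no sample size for the order analysis. The nearest figure is the 21 positives per condition for 95% v 70% at 90% power. It reproduces with the two-sided arcsine formula: h = 2·arcsin√0.95 − 2·arcsin√0.70 = 0.708, and n = ((1.960 + 1.282)/0.708)² ≈ 20.9, so 21.

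**Expected discordant pairs.** Let b be swab+/DDT− and c be swab−/DDT+ among clinician-positives, with device errors independent.

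1. *Order effect on both devices (95% first, 75% second).* In A, P(b) = 0.95 × 0.25 = 0.2375 and P(c) = 0.05 × 0.75 = 0.0375. In B the two are exchanged. With 45 per sequence, pooled b = 45 × (0.2375 + 0.0375) = 12.4, and pooled c is the same. McNemar compares b with c and sees nothing.

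2. *Device difference, no order effect (swab 95%, DDT 80%).* In both sequences P(b) = 0.95 × 0.20 = 0.19 and P(c) = 0.05 × 0.80 = 0.04. With 90 positives, b = 17.1 and c = 3.6. McNemar rejects although order does nothing.

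3. *Order effect on one device (DDT 95% throughout; swab 95% in A, 75% in B).* With 45 per sequence, b = 45 × (0.95 × 0.05 + 0.75 × 0.05) = 3.8 and c = 45 × (0.05 × 0.95 + 0.25 × 0.95) = 12.8. A swab at 85% in both sequences gives b = 90 × 0.85 × 0.05 = 3.8 and c = 90 × 0.15 × 0.95 = 12.8. The pooled tables have the same expectation, so the test cannot tell the two situations apart.

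**Rejection rates** of the exact McNemar test pooled over A and B (simulation, good to about two percentage points):

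| Assumed truth | 30 (STI) | 35 (HPV) | 90 (BV) |
|---|---|---|---|
| Order only, 95% first / 75% second | 1–2% | 1–2% | 1–2% |
| Device only, 95% v 80% | 25% | 32% | 82% |
| Device only, 95% v 90% | 2% | 3% | 16% |

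In scenario 3 the rate runs from about 10% (30 positives) to 53% (90 positives).

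**What an A v B comparison can do.** For an order effect of 95% v 70% on both devices, Fisher's exact test on DDT sensitivity rejects in about 27% of runs at 15 per sequence and 86% at 45. A Mainland-Gart test (discordant pairs by sequence) rejects in about 53% and 99%. Pooled McNemar rejects in about 1% at both.

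Normal-approximation power is Φ[(|p₁ − p₂|√n − 1.96√(2p̄(1 − p̄))) / √(p₁(1 − p₁) + p₂(1 − p₂))]. With p̄ = 0.825 and n = 15 this is Φ[(0.968 − 1.053)/0.507] = 43%. It is 48% at n = 17 and 89% at n = 45. Fisher's test is more conservative than this, as the 27% shows. For 95% v 70%, 80% power needs 36 positives per sequence and 90% needs 47.

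**The case against.** Several points on the other side stand. McNemar is not blind to every order effect: in scenario 3 it can reject. A reader might infer that it can never detect one, but that is exact only when both devices are affected alike. In other cases the difficulty is confounding with device.

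A reader might also infer that the randomisation is wasted. The documents do not support that. They state no sole purpose for it, and randomising order still counterbalances it, so pooled DDT results and the DDT v self-swab contrast are not tied to one fixed sequence. What is missing is its use in the order analysis.

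The false-signal rates depend on the assumed device gap. Section 8.3 plans on a DDT sensitivity of 95%. If the devices differ by only five points, the rate is small except for BV.

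It could be argued that the separate-group analyses cover A and B, since the protocol uses Group for both divisions. The context in sections 8.2.1, 8.3 and 8.5 points to Groups 1 and 2. Even on the other reading there would be two device comparisons with no test between them.

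The plea that detail is left to a SAP does not help. Section 8.1 says there is none, and section 8.2.2 names a specific test for this objective.

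**Conclusion.** The stated analysis does not answer the stated objective. As written, a symmetric order effect would be missed, a one-device effect could not be separated from a device difference, and a pure device difference could be reported as an effect of order. The structural point needs no effect-size assumption. The rejection rates rest on independent device errors, the section 8.3 prevalences with no losses, an even split by sequence, and the assumed sensitivities. They were worked for sensitivity; the same reasoning applies to specificity among clinician-negatives.

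This should be corrected, but its reach is limited. Order is one of several secondary objectives, and the sample size is not built on it. The DDT sensitivity estimates and the tests against 70% do not depend on it. A reader should not infer that the primary analysis is compromised, or that a corrected test would settle the order question for STI or HPV.

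**What to change.** In section 8.2.2, replace the order analysis with a comparison by randomised sequence:

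- For each condition and each device, compare sensitivity (clinician-positives) and specificity (clinician-negatives) between Groups A and B, with a risk difference, 95% confidence interval and Fisher's exact test. Both devices are needed: in scenario 3 only the self-swab comparison carries the effect.
- Optionally add a Mainland-Gart test on DDT/self-swab discordant pairs by sequence.
- Keep McNemar and kappa, relabelled as the DDT v self-swab comparison.
- State that the order result is exploratory, is to be read from the interval, and that a non-significant test does not show absence of an order effect.
- Where groups are pooled or analysed separately, say whether 1/2 or A/B is meant.

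The cost is protocol wording and a few lines of code. The allocation and all three sample results are already collected. The change is best made before results by sequence are seen, and recorded as section 8.9 requires.
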